## **RANDOMIZATION**

Participants will be randomly assigned to one of two study groups. Randomization assignments will be determined prior to initiation of the study using a random size permuted block design. Randomization will be stratified by age group with participants divided into 2 age groups of 18-49 years and 50-65 years. After obtaining informed consent, the signed informed consent document will be faxed to the investigational pharmacy. Upon receipt, the investigational pharmacy will begin preparation of the study material infusion. Assignment will be communicated electronically using Medrio randomization system. Once the study drug material is prepared, it will be sent to the bedside for administration via the bedside nurse under the oversight of one of the site investigators and/or study coordinator. After

baseline hemodynamic assessments, participants will be randomized to either placebo or citrulline in a 1:1 fashion stratified by age group. The participants, nurses, physicians, study coordinators and investigators will remain blinded to whether participants are receiving placebo or L-citrulline throughout the study. The investigational pharmacy will be unblinded and will be responsible for maintaining the blinding of investigators, participants, nurses, and primary medical team. The investigational pharmacy will deliver the correct infusion(s) to the patient's bedside every 24 hours. The placebo and study drug solutions will be identical appearing on delivery to the ICU where the drug will be administered.

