### Statistical Method for the Primary Clinical Efficacy Endpoint

Kaplan-Meier estimates of the survival functions will be graphically displayed for each treatment group. Kaplan-Meier quartiles (25th percentile and median) with two-sided 95% confidence intervals will be calculated if applicable. In addition, time to intubation will be summarized via displaying number of

subjects at risk, the percent of subjects that are censored, and Kaplan-Meier event rates with two-sided 95% confidence intervals.

A log-rank test stratified by the randomization stratification factor (age group) will be used to compare the time to intubation of the two treatment groups. The hazard ratio of IV Citrulline compared with placebo and its corresponding two-sided 95% confidence interval will be estimated using a Cox proportional hazards (PH) model with treatment groups as the independent variable and stratified by the age group.

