### **Statistical Method for the Secondary Clinical Efficacy Endpoints**

#### ***All-cause Hospital Mortality***

All-cause, hospital mortality, defined by whether the patient was discharged from the hospital alive or deceased, will be analyzed via two statistical methods. The proportion of patients who have died by

hospital discharge will be analyzed using a Fisher's Exact Test. Additionally, time to death will also be analyzed using Kaplan-Meier estimates of the survival functions. A log-rank test will be used to compare time to death for the two treatment groups. The hazard ratio of IV Citrulline compared with placebo and its corresponding two-sided 95% confidence interval will be estimated using a Cox proportional hazards (PH) model with treatment groups as the independent variable.

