#### ***Requirement for Intubation and Invasive Mechanical Ventilation***

We will provide summary statistics (frequency and percentages) of the proportion of patients that require intubation and invasive mechanical ventilation by treatment groups. We will test the difference in proportion requiring intubation and invasive mechanical ventilation using Fisher's exact test.

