#### ***Length of ICU Stay***

ICU length of stay (LOS) will be defined in days as the time from study enrollment to the day ICU discharge orders are written, regardless of when the patient physically leaves the ICU. Comparison will be made between the two groups for total ICU length of stay which will include any days of ICU re-admission prior to hospital discharge. We will consider ICU LOS a count measure and has the potential to follow a skewed distribution. Initially, we will assess the distributional assumption. We will use a generalized linear model (GLM) to compare the expected ICU LOS between the two treatment groups (placebo and intravenous citrulline). Specifically, we will use a negative binomial distribution and log-link to account for potential over-dispersion. We will report point estimates for the group mean difference along with a 95% confidence interval.

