### **Statistical Method for the Safety Endpoint (Hemodynamic status)**

The vasopressor dependency index (VDI) is a continuous variable calculated by dividing vasopressor index (summation of all pressors) by the mean arterial blood pressure (MAP). VDI will be calculated at baseline (immediately before start of the infusion), 2 hours after completion of the bolus, and every 4 hours during the infusion. We will report descriptive statistics (mean  $\pm$  SD) of baseline and worst VDI separately for each treatment group. Worst VDI will be compared between groups using an analysis of covariance (ANCOVA) with the baseline VDI as the covariate.

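### The secondary tests omit the age-group stratification used in randomisation and in the primary analysis: a minor inconsistency that makes them conservative if age is prognostic

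*SAP*

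**What the plan says.** SAP, Randomization: "Randomization will be stratified by age group with participants divided into 2 age groups of 18-49 years and 50-65 years". Protocol 5.1.1 says the same.

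The primary analysis follows the design: "A log-rank test stratified by the randomization stratification factor (age group) will be used to compare the time to intubation", and its Cox model is stratified by age group too.

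The secondary methods do not mention age group:

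- Hospital mortality, as a proportion: "hospital discharge will be analyzed using a Fisher's Exact Test".
- Time to death: "A log-rank test will be used to compare time to death for the two treatment groups"; the hazard ratio "will be estimated using a Cox proportional hazards (PH) model with treatment groups as the independent variable".
- Intubation and ventilation: "We will test the difference in proportion requiring intubation and invasive mechanical ventilation", by Fisher's exact test. The two other intubation proportions follow the same plan.
- ICU stay: "We will use a generalized linear model (GLM) to compare the expected ICU LOS between the two treatment groups", with a negative binomial distribution. Hospital stay follows the same plan.
- Duration of mechanical ventilation: a zero-inflated Poisson model, with no age term named.
- Plasma citrulline, arginine, ornithine and NOx: a mixed model with treatment, time and their interaction.
- Haemodynamics: "Worst VDI will be compared between groups using an analysis of covariance (ANCOVA) with the baseline VDI as the covariate".

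SAP Table 3 expects age to be an independent covariate, intends to assess it in two groups, and refers to the secondary endpoints for the fuller list of outcomes. The section on covariates for the primary clinical endpoint then applies Table 3 to time to intubation only.

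The SAP Sample Size section gives 80% power for mortality, 50% versus 17% with 60 patients, by a two-sided pooled z-test.

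**The concern.** Stratified randomisation balances age between the arms. If age also predicts the outcome, an analysis that ignores it carries between-stratum variation in its standard error that the design has already removed from the treatment comparison. Type I error then falls below nominal and some power is lost. The secondary endpoints also go through a Hochberg adjustment, so conservative p-values cost more.

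The SAP states an intention about age in Table 3, carries it out for one endpoint, and gives no reason for leaving it out of the others. If age is added after unblinding, the change will look data-driven.

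**Working it through.** **Inputs from the SAP.** Mortality 50% (placebo) and 17% (citrulline); 60 patients, so 30 per arm; two-sided 0.05; two age strata.

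**Assumptions (not in the documents).** Age odds ratio 1 to 10 for death, or hazard ratio 1 to 5 for time to death, older versus younger; half the patients in each stratum unless stated; 60 days of follow-up and exponential times for the log-rank simulations.

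**Step 1: the plan's own figure.** Pooled z-test with mean rate (0.50 + 0.17)/2 = 0.335:

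z = [0.33 × √30 − 1.96 × √(2 × 0.335 × 0.665)] / √(0.50 × 0.50 + 0.17 × 0.83) = (1.807 − 1.308)/0.625 = 0.80, so power = 78.8%.

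Exact enumeration of the same test gives 79.0%. The stated 80% is reproduced to within about 1 point.

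**Step 2: the test actually planned.** Summing the two binomial probabilities over all tables with Fisher p ≤ 0.05 gives 70.8% power, about 8 points below the z-test. Fisher's true size is 2.7% at a common rate of 50% and 2.6% at 33.5%; the z-test has 5.2% and 4.8%. No age effect enters this step.

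**Step 3: stratification alone, mortality proportion.** Overall rates held at 50% and 17%, 20,000 simulations, unstratified chi-square against Cochran-Mantel-Haenszel (CMH) without continuity correction:

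| Age odds ratio | Unstratified | Stratified | Gain (points) |
|---|---|---|---|
| 1 | 78.5% | 78.8% | 0.3 |
| 2 | 79.2% | 80.2% | 1.0 |
| 3 | 79.5% | 81.7% | 2.2 |
| 5 | 79.8% | 83.7% | 3.9 |
| 10 | 81.5% | 87.6% | 6.1 |

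**Step 4: stratification alone, time to death.** Treatment hazard ratio = ln(0.83)/ln(0.50) = 0.269, 20,000 simulations of the log-rank test:

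| Age hazard ratio | Unstratified | Stratified | Gain (points) |
|---|---|---|---|
| 1 | 79.6% | 79.4% | −0.2 |
| 2 | 79.0% | 80.1% | 1.1 |
| 3 | 78.0% | 81.3% | 3.3 |
| 5 | 75.0% | 81.9% | 6.9 |

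With 80% of patients in one stratum and hazard ratio 3, the gain is 1.3 points (79.5% to 80.8%). With only about 8 deaths and age not prognostic, stratifying loses 0.5 to 0.8 points (39.2% to 38.6% or 39.4% to 38.6%, depending on the split; differences taken before rounding). The simulated type I error of the unstratified log-rank falls from 4.9% at age hazard ratio 1 to 2.4% at 5; stratified, it stays at about 5 to 6%.

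**Step 5: separating the two effects.** Take death rates of 35% to 10% in the younger and 65% to 24% in the older stratum (averages 50% and 17%; age odds ratio about 3):

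- Fisher, unstratified: 71.2%
- chi-square, unstratified: 79.7%
- CMH, age-stratified: 82.1%

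The total gap is 82.1 − 71.2 = 10.9 points. Of this, 79.7 − 71.2 = 8.5 come from leaving Fisher's test and 82.1 − 79.7 = 2.4 from stratifying.

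The version of the stratified test matters. In the same scenario the continuity-corrected CMH has 73.0%, the fully exact stratified test about 73 to 74%, and its mid-p version 80.1%.

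**The case against.** The strongest defence is that nothing here can create a false positive. The primary test is stratified correctly, the affected endpoints are secondary in a phase II trial of 60 to 66 patients, and an unstratified analysis errs on the conservative side. The SAP is openly cautious about adjustment at this sample size: it declines a simultaneous covariate model for the primary endpoint and allows re-categorisation if a model fails to converge. Fisher's test is a recognised choice when counts may be small. All of this stands, and it sets the severity.

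Three stronger readings are tempting, and the documents do not support them:

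- *That ignoring the strata costs about 11 points of power.* A direct comparison of Fisher with stratified CMH suggests this, but about 8.5 of those points come from Fisher's discreteness.
- *That stratifying is free.* It can lose a fraction of a point when deaths are few and age is not prognostic. The SAP calls age only a likely covariate and gives no figure for its effect within 18 to 65 years.
- *That every secondary analysis is affected.* Length of oxygen therapy has a heading but no method, and adverse events are only tabulated. The power figures above are for mortality; none was computed for length of stay, the mixed model or the vasopressor dependency index.

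The defence does not explain why Table 3 names the secondary outcomes while no secondary method uses age, or why the log-rank test is stratified for intubation but not for death.

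**Conclusion.** The point holds as a minor inconsistency. The specified secondary tests do not follow the randomisation or Table 3, and they are conservative if age is prognostic. For mortality, stratifying is worth about 0 points of power with no age effect, about 1 to 3 at an odds or hazard ratio of 2 to 3, and about 4 to 7 for a strong effect (odds ratio 5 to 10, hazard ratio 5). These sizes rest on the assumed age effect, stratum split and follow-up.

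The mismatch between the power statement and the planned mortality test does not depend on the age effect: about 71% for Fisher's test, against a stated 80% that reproduces at about 79%. It should be reported as a separate matter and not used to size the stratification point. The validity of the primary analysis is not in question.

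**What to change.** Before unblinding, amend the SAP as follows:

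- Stratify the time-to-death log-rank test and Cox model by age group, as for the primary endpoint.
- For hospital mortality and the intubation proportions, replace Fisher's test with an age-stratified CMH test without continuity correction. If cells are sparse, use the mid-p version; the fully exact version gives back most of the gain.
- Add age group as a factor in the length-of-stay, ventilation-duration and biochemical mixed models and in the ANCOVA of worst vasopressor dependency index.
- Where age group is left out on purpose, say so and give the reason.
- Base the mortality power statement on the test that will be used.

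The cost is about one line per method and no new data, with a possible loss of under 1 point of power if age is not prognostic and deaths are few.

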#### ***Requirement for Intubation and Invasive Mechanical Ventilation***

We will provide summary statistics (frequency and percentages) of the proportion of patients that require intubation and invasive mechanical ventilation by treatment groups. We will test the difference in proportion requiring intubation and invasive mechanical ventilation using Fisher's exact test.

#### ***Difference in Proportion of Patients Intubated***

To compare the proportion of patients intubated across the two treatment groups, we will follow the same analytical plan for the requirement for intubation and invasive mechanical ventilation outcome.

#### ***Difference in Proportion of Patients Intubated and on MV***

To compare the proportion of patients intubated across the two treatment groups, we will follow the same analytical plan for the requirement for intubation and invasive mechanical ventilation outcome.

#### ***Length of ICU Stay***

ICU length of stay (LOS) will be defined in days as the time from study enrollment to the day ICU discharge orders are written, regardless of when the patient physically leaves the ICU. Comparison will be made between the two groups for total ICU length of stay which will include any days of ICU re-admission prior to hospital discharge. We will consider ICU LOS a count measure and has the potential to follow a skewed distribution. Initially, we will assess the distributional assumption. We will use a generalized linear model (GLM) to compare the expected ICU LOS between the two treatment groups (placebo and intravenous citrulline). Specifically, we will use a negative binomial distribution and log-link to account for potential over-dispersion. We will report point estimates for the group mean difference along with a 95% confidence interval.

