7.1.4 Mortality, Hospital, and ICU Length of Stay Assessment

Participant survival will be assessed at hospital discharge. ICU length of stay will be the total number of days the participant spends in the ICU from time of enrollment to hospital discharge. Re-admissions to the ICU during the initial hospital stay will be added to the initial ICU length of stay to determine a total number of ICU days. Hospital length of stay will be calculated as the number of days from enrollment to

hospital discharge. Once the patient is discharged from the hospital (to any disposition including home, home with help, rehab, or another hospital) or dies, hospital days will cease. Subsequent re-admissions to the hospital or ICU after hospital discharge will not be added to the hospital or ICU lengths of stay, respectively.

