7.2.3 Clinical Outcome Assessments

ICU length of stay will be calculated in days from time = 0 to the earlier of ICU discharge or death. Any re-admissions to the ICU during the hospital stay will add days to ICU length of stay. Hospital length of stay will be calculated in days from time = 0 until the earlier of hospital discharge or death. A follow up at D28 and D60 will further evaluate the stated clinical outcomes.

Concomitant medications and adverse events will continue to be monitored and recorded in the CRF for the duration of the participant's hospital stay.

See the Schedule of Procedures in Appendix A for further details.

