10.6.1 Secondary Clinical Endpoints

All-cause, hospital mortality, defined by whether the patient was discharged from the hospital alive or deceased, will be analyzed via two statistical methods. The proportion of patients who have died by hospital discharge will be analyzed using a Chi-square analysis or Fisher's Exact Test, if needed. In addition, time to death will also be analyzed using a log-rank method of a Kaplan-Meier analysis. ICU length of stay (LOS) will be defined in days as the time from study enrollment to the day ICU discharge orders are written, regardless of when the patient physically leaves the ICU. Comparison will be made between the two groups for total ICU length of stay which will include any days of ICU re-admission prior to hospital discharge. Hospital length of stay will be defined as time from study enrollment to first hospital discharge. We will consider both ICU LOS and hospital LOS as count measure and has the potential to follow a skewed distribution. Initially, we will assess the distributional assumption. We will use a generalized linear model (GLM) to compare the expected ICU LOS and hospital LOS between the two treatment groups (placebo and intravenous citrulline). Specifically, we will use a negative binomial distribution and log-link to account for potential over-dispersion. We will report point estimates for the group mean difference along with a 95% confidence interval. Overall duration of mechanical ventilation will be modeled with zero-inflated Poisson or negative binomial method using consent and post-infusion start time for two separate analysis.

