#### ***Length of Hospital Stay***

Hospital length of stay will be defined as time from study enrollment to first hospital discharge. We will follow the same analytical plan for the length of ICU stay outcome.

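### ICU length of stay has three conflicting definitions, and two of them, read literally, start the clock before the patient enters the ICU

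*SAP*

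**What the plan says.** Three definitions of ICU stay are in the current text.

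- **Protocol 7.1.4:** "ICU length of stay will be the total number of days the participant spends in the ICU from time of enrollment to hospital discharge". Re-admissions during the same hospital stay are added.
- **Protocol 7.2.3:** "ICU length of stay will be calculated in days from time = 0 to the earlier of ICU discharge or death". Time 0 is the start of study infusion (Protocol 7.2.2). Re-admissions add days.
- **Protocol 10.6.1 and SAP, Length of ICU Stay:** the protocol wording is "ICU length of stay (LOS) will be defined in days as the time from study enrollment to the day ICU discharge orders are written"; in the SAP, ICU stay likewise "will be defined in days as the time from study enrollment to the day ICU discharge orders are written". Physical departure is expressly disregarded. Both then compare a "total ICU length of stay which will include any days of ICU re-admission prior to hospital discharge".

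All three work in days. The endpoint lists in Protocol 2.0, SAP Table 1 and SAP Secondary Clinical Endpoints give ICU stay in hours.

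The inclusion criteria (Protocol 6.2) require a patient on the floor and not intubated. The planned comparison is a negative binomial model with log link, reporting a group mean difference with a 95% confidence interval.

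**The concern.** The definitions differ in where the clock starts, where it stops and what happens at death. Two programmers working from different sections would derive different values for the same patient.

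The start point matters most. An interval that begins at enrolment or at infusion start measures time until the patient leaves the ICU. It measures time in the ICU only if the patient was already there at the start. For a floor patient who deteriorates later, the wait before ICU entry is scored as ICU time.

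The trial's hypothesis is that citrulline delays, and may prevent, invasive ventilation. If it delays ICU entry in the same way, the delay would be recorded as a longer ICU stay. The secondary outcomes also share a Hochberg adjustment (SAP, Statistical Significance), so a distorted p-value here can affect the decisions on others.

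**Working it through.** The plan gives no expected value, power or sample size for ICU stay, so there is no figure of its own to reproduce. The check compares the definitions and then applies simple arithmetic.

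**Definitions side by side**

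| | Start | End | Death | Never in ICU |
|---|---|---|---|---|
| Protocol 7.1.4 | ICU days only, counted from enrolment | hospital discharge | hospital days stop | not stated; 0 follows naturally |
| Protocol 7.2.3 | infusion start | ICU discharge | ends the stay | not stated |
| Protocol 10.6.1 and SAP | enrolment | day orders are written | not stated | not stated |

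**One patient.** Let W be the time from clock start to ICU entry and L the time in the ICU, in elapsed days, with enrolment and time 0 taken as the same. The literal SAP value is W + L; the 7.1.4 value is L. With entry on day 6 and orders on day 9, W = 6 and L = 3.

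- SAP: 6 + 3 = 9
- 7.1.4: 9 − 6 = 3

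The 7.2.3 clock also gives 9 if the patient leaves on day 9. Counting calendar days instead, days 6 to 9 make 4 under 7.1.4, so the counting convention also needs stating. A re-admission on days 12 to 14 brings the 7.1.4 total to 3 + 2 = 5. The SAP total becomes 9 + 2 = 11 if only the re-admission days are added, or 14 if the clock runs to the last order.

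**Two arms, illustration only.** Assumptions:

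- ICU entry occurs at the sample-size section's times to intubation, 3 days (placebo) and 6.5 days (citrulline). The 6.5 is read as the citrulline time because 3/6.5 = 0.46, the stated hazard ratio.
- L = 10 days in each arm. This borrows the median ventilation time in the case series in Protocol 3.4 (interquartile range 7 to 12), which is not an ICU stay.

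The scored ratio, citrulline to placebo, is (6.5 + L)/(3 + L).

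| L (days) | Placebo | Citrulline | Ratio |
|---|---|---|---|
| 5 | 8 | 11.5 | 1.44 |
| 7 | 10 | 13.5 | 1.35 |
| 10 | 13 | 16.5 | 1.27 |
| 12 | 15 | 18.5 | 1.23 |

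The true ratio is 1.00 in every row. Three variations at L = 10:

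- **Half already in the ICU at the start:** 10 + 0.5 × 3 = 11.5 against 10 + 0.5 × 6.5 = 13.25, ratio 1.15.
- **Citrulline also prevents entry, non-entrants scored 0:** the scored ratio is 1.27 times the true one. It reaches 1.00 at a true ratio of 13/16.5 = 0.79, a 21% relative fall in ICU entry. With smaller falls, a true benefit is scored as harm.
- **Equal entry rate and timing:** if everyone enters at day 3 and true stays are 10 against 8, the scores are 13 against 11. The difference stays at 2 days, but the ratio moves from 0.80 to 11/13 = 0.85.

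**The case against.** The strongest reply is that the SAP wording is loose and was never meant to score floor time. Protocol 7.1.4 uses enrolment to hospital discharge as a window around ICU days, and the SAP could be read the same way. Its next sentence, on re-admission days, points to ICU days as the intended quantity. That reading is plausible, but it does not remove the fault. The SAP states an interval with a start and an end, which conflicts with 7.1.4, and intent should be settled in writing before unblinding.

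Other parts of the reply stand:

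- Protocol 7.2.3 already ends ICU stay at death; the SAP only fails to carry that rule over.
- Patients already in the ICU at the start add no floor time. Protocol 5.1.1 and SAP Randomization mention delivery of study drug to the ICU, so there may be some; their share is not given.
- The SAP does choose an end rule, the written order. The difficulty is that 7.1.4 uses a different one.

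A reader might infer that hospital stay also lacks a death rule, because the SAP says "Hospital length of stay will be defined as time from study enrollment to first hospital discharge". The documents do not support that. In Protocol 7.1.4, once the patient is discharged "or dies, hospital days will cease"; Protocol 7.2.3 also stops at death; and the SAP mortality section treats discharge as covering patients "discharged from the hospital alive or deceased". Only a cross-reference is missing.

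**Conclusion.** The conflict is real and is in the current text of both documents. Read literally, the SAP and Protocol 10.6.1 count floor time as ICU time for any patient who enters the ICU after enrolment, and Protocol 7.2.3 does the same from infusion start. Only 7.1.4 avoids this. The single-patient result, 9 against 3, needs only an elapsed-day convention.

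A reader might conclude that the plan biases this endpoint against citrulline by about 27%. The documents do not support that. The figure requires a 3.5-day delay in ICU entry, entry at the time of intubation, 10 ICU days per arm and everyone entering from the floor. None of these is given for ICU stay. The direction is against citrulline if it delays entry; with equal entry rate and timing the effect is dilution. The group-level size is unknown.

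ICU stay is a secondary endpoint. The primary analysis and the sample size are unaffected, but the wording should be corrected before database lock.

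**What to change.** Use the 7.1.4 definition in SAP Length of ICU Stay and in Protocol 10.6.1 and 7.2.3. State that:

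1. ICU stay is time in the ICU, summed over admissions, from enrolment to hospital discharge or death, with the death rule as in 7.2.3.
2. A patient never admitted to the ICU scores 0.
3. Each ICU admission ends by one rule, either orders written or physical departure, whichever the collected data support.
4. One unit and one counting convention apply in Protocol 2.0, 7.1.4, 7.2.3 and 10.6.1, SAP Table 1, SAP Secondary Clinical Endpoints and SAP Length of ICU Stay.

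A cross-reference from SAP Length of Hospital Stay to the protocol's death rule would be useful. Keep the planned negative binomial comparison. ICU-free days could be added as a sensitivity analysis, but that is optional and not part of this fix.

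The cost is wording, plus a protocol amendment with the IRB notification that Protocol 11.2 foresees. ICU status is already scheduled on Days 1 to 11 and from Day 12 to discharge (Appendix A), which supports a count in days. The documents do not show that times of discharge orders are captured; confirm this before choosing that end rule or hours as the unit.
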